community partners will provide two coupon sheets per household during weeks 1-6 of the intervention. Participants may redeem coupons at farmers' markets at a frequency of their choice (e.g., redeem coupons weekly or redeem several weeks' worth of coupons simultaneously). Participants in the FMNCP group will be invited to participate in nutrition skill-building activities (e.g., cooking classes) offered by community partners throughout the intervention period, although participation is not required (this is consistent with the existing FMNCP). The types and frequency of nutrition skill-building activities offered vary across community partners. For the duration of the study, the control group will not receive coupons nor be eligible to participate in nutrition skill-building activities but will be eligible to participate in the BC FMNCP the following farmers' market season. As participants in the control group already receive other supports from community partners, they will continue to meet with their community partner as they normally would throughout the intervention period.

Data collection

Data will be collected from the FMNCP and control groups at three time points: Time 1: baseline (0 weeks), Time 2: immediately post-intervention (10-15 weeks), and Time 3: 16 weeks post-intervention (26-31 weeks). At each time point, participants will complete a questionnaire assessing sociodemographic characteristics, health-related variables, and secondary and exploratory outcomes, followed by a 24-hour dietary recall to assess diet quality. The questionnaire and dietary recall will be integrated within a web-based platform developed and pilot tested by the researchers [116]. A second dietary recall will be completed 2-5 days later to better estimate usual intake and account for within-individual variation in diet quality. All participants will receive cash incentives valued at \$20 at baseline and \$40 at each Time 2 and 3. Participants will also receive small gifts prior to data collection at Time 2 and 3, which will serve as a reminder for the upcoming data collection.

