The HEI-2015 encompasses thirteen dietary components to assess overall diet quality,[161] including nine 'adequacy' components (recommended foods/nutrients, including total fruits, whole fruits, total vegetables, greens and beans, whole grains, dairy, total protein foods, seafood and plant proteins, fatty acids) and four 'moderation' components (foods/nutrients recommended to limit, including refined grains, sodium, added sugars, saturated fats). Component scores are density-based and, therefore,

independent of energy intake.[161, 163] Diet quality (total HEI-2015 scores and subscores) will be calculated using the simple HEI scoring algorithm.[161] This method provides scores at the individual level and can, therefore, accommodate the multi-level nature of our data and include covariates.[161] HEI-2015 scores will be calculated using three nutrient databases linked to the ASA24-Canada-2018:[173] the Canadian Nutrient File and the U.S. Department of Agriculture's (USDA) Food and Nutrient Database for Dietary Surveys to convert dietary intakes to energy and nutrient intakes, and the USDA Food Patterns Equivalents Database to convert dietary intakes to dietary constituents (e.g., fruits) and measurement units consistent with HEI-2015 scoring standards (e.g., cup-equivalents of fruit).[162, 163, 174, 175] Ratios for each of the dietary constituents (e.g., quantity of fruit per 1000 kcal) will be calculated for each participant and scored using HEI-2015 scoring standards. The total score for each participant will be derived by adding the scores for intake of 'adequacy' and 'moderation' components with possible scores ranging from 0-100. A higher score indicates a higher quality diet.[161]

Statistical analyses

Descriptive analyses will be conducted to examine participant characteristics by group at each time point. Characteristics of study completers (i.e., provided data at Time 3) and non-completers will also be compared.

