Analyses will be intention-to-treat, in which participants will be analysed within the groups to which they were randomized regardless of adherence (e.g., failure to redeem coupons) or dropout. The analyses will include all participants who provided data at baseline. Repeated measures mixed-effect regression will assess differences in changes in mean HEI-2015 scores, HEI-2015 subscores, mental well-being, sense of community, and subjective social status between the FMNCP and control groups immediately post-intervention and 16 weeks post-intervention. Multinomial logistic regression will be used to assess

differences in the odds of experiencing household food insecurity and malnutrition risk for the FMNCP group compared to the control group immediately post-intervention and 16 weeks post-intervention. Statistical models will include intervention group (FMNCP vs control), time from baseline, intervention-by-time interaction, blocking variables (i.e., sex, rural/urban, pregnancy, breastfeeding), baseline values of the outcome, data collection mode (online, phone), household size, and place of data collection (community partner, other) as fixed effects covariates. Participant-specific (i.e., repeated measures) and rural/urban variations in outcomes will be modeled using random effects. Models will also include covariates specific to each outcome to increase the precision of estimates.[95] For the primary outcome of overall diet quality, models will include children living in the home (yes, no), sex, age, BMI, marital status, race/ethnicity, perceived health, smoking, day of dietary recall completion, and dietary recall number (i.e., dietary recall 1 or 2). Models that are and are not adjusted for an indicator of energy intake misreporting (the ratio of reported energy intake to total estimated energy expenditure) will be presented. Adjusted group differences (i.e., FMNCP vs control) in outcomes will be estimated using 95% confidence intervals and corresponding p-values.

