Subgroup analyses will examine whether the impact of the intervention on primary and secondary outcomes differs according to age group or sex. Dose-response analyses will examine whether the impact of the BC FMNCP on overall diet quality depends on the number of coupons redeemed and the number of nutrition skill-building activities attended. Interactions will be retained in statistical models if $p < 0.10$. Analyses will be conducted in Stata (v15.1, Stata Corp, TX, USA), with $p < 0.05$ indicating statistically significant differences between groups.

Missing data

Missing data will be handled using full information maximum likelihood under a missing at random assumption. We will also attempt to minimize missing data by reviewing all data within 24 hours of receipt and by contacting participants to fill-in missing or implausible responses within 48 hours. Participants who drop out of the study will be asked to provide reasons for drop out to assess the plausibility of a missing at random assumption.

Sensitivity analyses

Monte Carlo Markov Chain multiple imputation, inverse probability weighting and available case analysis will be used in a sensitivity analysis to investigate the impact of different assumptions about missing data on estimated program impacts.[176-178] Given the possibility of non-random attrition, pattern mixture methods models [179] will be used to explore the robustness of study findings to the assumption that data were missing not at random.[180]

Sample size calculation

The sample size was calculated from a RCT that investigated the impact of a fruit and vegetable rebate on HEI-2010 scores in low-income participants in the U.S.,[95] and a cross-sectional study that assessed average diet quality scores in disadvantaged Canadians.[36] In the RCT, diet quality in the intervention group was 4.7 points higher (95% CI 2.4, 7.1) at follow-up compared to controls.[95] This difference can be translated to, for example, an additional half serving of fruit per day, which is clinically meaningful and achievable.[107, 165] Assuming a type I error of 5%, an attrition rate of 30% by the 26- to 31-week follow up, and potential design effects based on sampling within different communities (estimated at 1.1, or an inflation of 10%), 264 participants are required for 80% power to detect a 4.7-point difference in diet quality.

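### The sample size allows 10% for community clustering, but the analysis model has no community or partner term; the interval is too narrow only if the programme effect varies between partners

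*Combined protocol and SAP*

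**What the plan says.** **Sample size calculation.** The 264 participants include an allowance for "potential design effects based on sampling within different communities (estimated at 1.1, or an inflation of 10"%). The target is stated as "264 participants are required for 80% power to detect a 4.7-point difference in diet quality".

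**Statistical analyses.** The fixed effects are arm, time, arm-by-time, the blocking variables (including rural/urban), the baseline value, collection mode, household size, place of data collection and outcome-specific covariates. On random effects the plan says: "Participant-specific (i.e., repeated measures) and rural/urban variations in outcomes will be modeled using random effects". Neither community nor community partner is listed. Place of data collection records whether someone answered at a partner site or elsewhere, not which partner. No cluster-robust variance is named. The Sensitivity analyses section deals only with missing data.

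**Recruitment, Randomization and Intervention.** About 15 communities are planned. Participants are randomised individually 1:1, stratified by sex, rural/urban, pregnancy and breastfeeding, but not by community or partner. Partners hand out the coupons and offer the activities, and "The types and frequency of nutrition skill-building activities offered vary across community partners". Controls receive neither.

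**Healthy Eating Index-2015.** The scoring method is chosen partly because it can "accommodate the multi-level nature of our data", but community is not named as a level.

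**The concern.** The design pays for a source of variance that the analysis never estimates. Rural/urban does not fill the gap. Two levels cannot carry the variation among about 15 communities, and a random effect on a factor that is already fixed adds little or nothing. As written, it is also a term for variation in outcome level, not in programme effect.

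The component that matters is specific. A community level shared by both arms largely drops out of an individually randomised comparison. A programme effect that differs by partner does not drop out, because the partner delivers the programme to one arm only. If such variation exists and the result is read as the average effect of the programme beyond these sites, the planned standard error is too small.

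**Working it through.** **Inputs.** From Sample size calculation: "Assuming a type I error of 5%, an attrition rate of 30% by the 26- to 31-week follow up", 80% power, 4.7 points, design effect 1.1, total 264. From Recruitment: about 15 communities. Two-sided testing is assumed, since group differences "will be estimated using 95% confidence intervals and corresponding p-values". The outcome SD is not stated; one source is described only as "a cross-sectional study that assessed average diet quality scores in disadvantaged Canadians". The SD is therefore back-solved and is an assumption.

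**1. The plan's own figure.** 264 × 0.7 / 1.1 = 168, or 84 per arm. In the other direction, 84 × 1.1 / 0.7 = 132 per arm. Because no SD is given, 264 cannot be checked independently. From n = 2(z·SD/Δ)² per arm with z = 1.960 + 0.842 = 2.802:

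SD = 4.7 × √(84/2) / 2.802 = 10.87

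With rounding up, SDs of 10.81 to 10.87 give 84 per arm. Other ways of applying the inflations need 11.32–11.37 (multiplying by 1.3 for attrition) or 11.44–11.50 (a single factor of 1.4). For scale, SDs of 9, 10, 11, 12, 13 and 14 give totals of 184, 228, 272, 324, 382 and 440.

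**2. Standard errors.** Retained per arm: 264 × 0.7 / 2 = 92.4.

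- Without clustering: SE = 10.87 × √(2/92.4) = 1.60; 95% half-width 3.14.
- With 1.1: SE = 1.60 × √1.1 = 1.68; half-width 3.29.
- Ratio: √1.1 = 1.049, so the interval is about 5% too narrow if the 1.1 is real and left out.
- Type I error: 2Φ(−1.96/√1.1) = 6.2%; coverage 93.8%.

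The last two lines do not depend on the SD.

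**3. What effect variation does 1.1 represent?** If the programme effect has SD τ across 15 communities, it adds τ²/15 to the variance. Setting τ²/15 = 0.1 × 1.60² gives τ = √1.5 × 1.60 = 1.96 HEI points. An outcome SD of 9 would give 1.6 and an SD of 14 would give 2.5.

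**4. Simulation.** 184 retained participants, 15 communities, individual randomisation, a simple two-arm comparison that ignores community, 20,000 runs per row. It does not reproduce the planned repeated-measures model.

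| Shared-level ICC | Effect SD | Type I error |
|---|---|---|
| 0 | 0 | 5.1% |
| 0.009 | 0 | 5.0% |
| 0.05 | 0 | 5.0% |
| 0.10 | 0 | 4.8% |
| 0.009 | 1.96 | 6.2% |

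Shared community levels do no harm. Effect variation at the size of the plan's allowance does a little.

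**5. Price of allowing for it.** With 15 communities and about 14 degrees of freedom, the multiplier is 2.145 instead of 1.96.

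- Half-width: 2.145 × 1.68 = 3.60, against 3.14, so about 15% wider. About 5% comes from the variance and the rest from the degrees of freedom.
- Power at 4.7 points: noncentral t with noncentrality 4.7/1.68 = 2.80 on 14 df gives about 74%, against the planned 80%.
- Precision of the variance estimate: 184.8/15 = 12.3 retained per community. In a simulation at effect SD 1.96 with a moment estimator, the slope variance came out as zero in about 45% of trials.

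**The case against.** A reader might infer that the plan expects clustering and then leaves it out, so that its interval is wrong. The documents do not support that. The design effect is called potential and is tied to sampling within communities. Nowhere does the plan say that the programme effect will differ between them. The 1.1 may simply be a conventional margin for shared levels, and then the simpler model keeps its 5% error rate. This objection stands.

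The harm also depends on the target. The objective is the programme's impact among low-income adults, and the communities are selected, not randomly sampled. The average effect in the participating communities is a legitimate target under individual randomisation and needs no random slope. That stands too, and it is the main reason not to insist on a random slope in the primary model.

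The evidence for effect variation is limited. Attendance at activities is optional, the coupon allotment follows a common household-size rule, and a dose-response analysis by coupons redeemed and activities attended is planned. That analysis looks at one likely source of variation but does not adjust the standard error.

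A reader might also extrapolate to larger effect SDs. Values of 3 or 4 points would give type I errors of about 7–8% or 9–10%, but they imply design effects of about 1.23 and 1.42. Nothing in the documents supports those values, so they carry no weight here.

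What survives is that the plan budgets for communities, has an intervention that varies by partner, and neither models that level nor explains its absence.

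**Conclusion.** The mismatch between the sample size and the analysis model is real. Its consequence is conditional and modest. If the entire 1.1 reflects a programme effect that varies between partners, the interval is about 5% too narrow and the type I error about 6.2% for the average effect over a wider population of sites. If the 1.1 reflects only shared community levels, there is no distortion.

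The 5% and 6.2% figures rest on the plan's 1.1 alone. The effect SD of about 2 HEI points rests in addition on the back-solved SD, on 15 communities of similar size, and on a single unadjusted follow-up comparison. Baseline adjustment would shrink the standard error, so the same 1.1 would then correspond to a smaller effect SD.

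The point deserves a correction to the plan, but it does not undermine the primary analysis.

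**What to change.** In Statistical analyses:

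1. Replace the rural/urban random effect with a random intercept for community partner (or community), and keep rural/urban as a fixed effect.
2. Prespecify a sensitivity analysis for the primary outcome, with either a random partner-by-arm slope or partner-clustered standard errors, using small-sample degrees of freedom in both cases. Report the between-partner SD of the effect.

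**Cost.** This changes wording only. Community of residence is collected and partners enrol every participant, so no new data collection appears necessary. The sample size stays at 264, since the 1.1 is already in it.

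**Downsides to state openly.** The intercept alone does not correct for variation in effect; only the sensitivity analysis addresses that. Its interval will be about 15% wider with about 14 degrees of freedom, and its power at 4.7 points about 74%. The loss is smaller if there are more partners than communities; the number of partners is not given. With about 12 retained participants per community the slope variance will be poorly estimated, so an estimate of zero should not be read as evidence that the effect is uniform.
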